Study Purposes and Objective

We propose to conduct a randomized clinical trial to determine the impact of three different types of psychosocial support for pre-operative joint replacement patients. This project will be conducted in an existing pain management program within the University of Utah Orthopedic Clinic which currently employs mental health professionals to teach patients preparing for surgery pain management strategies. We wish to evaluate the differential impact of three therapeutic approaches (i.e., mindfulness training, therapeutic suggestion, and CBT psychoeducation) by randomly assigning patients to one of the three approaches.

Aim 1. To assess the differential effects of a brief mindfulness training session versus therapeutic suggestion session or a CBT psychoeducational session on preoperative pain, anxiety, and pain medication desire for patients preparing for surgery as well as postoperative physical functioning.

Hypotheses: Mindfulness training and therapeutic suggestion will decrease pain, anxiety, and pain medicine desire as well as increase postoperative physical function to a significantly greater extent than CBT psychoeducation.

Participants

Inclusion criteria: English-speaking males or females 18 or older within the University of Utah Hospital system that are enrolled in the University Orthopedic Clinic's Joint Academy in preparation for a knee or hip replacement.

Exclusion criteria: Altered mental status due to delirium, psychosis, or pharmacological sedation as determined by clinical assessment conducted by a mental health professional.

How will participants be recruited or identified for inclusion in the study?

Patients enrolled in the University of Utah Orthopedic Center's Joint Academy will be recruited during the Joint Academy's standardized, 2-hour pre-operative information program.

At the time that the mental health professional makes contact with the potential participant, the patient will be presented with a fact sheet about the study, which the mental health professional will discuss with the patient. Their willingness to answer study questions and participate in the psychosocial supportive intervention with the mental health professional will indicate their consent.

Describe all the procedures chronologically, from screening/enrollment through study closeout, which will be completed in the research project.

Patients enrolled in the Joint Academy will be randomized to either a brief mindfulness training, therapeutic suggestion, or CBT psychoeducation condition (allocation ratio 1:1:1) using a pre-generated random number table, determining the type of psychosocial supportive intervention introduced during the Joint Academy's 2-hour information session. The visiting mental health professional will be notified of the random assignment prior to Joint Academy.

The patient will attend Joint Academy as part of standard care. At Joint Academy, the mental health professional makes will make contact with the potential participant, the patient will be presented with a fact sheet about the study, which the mental health professional will discuss with the patient. Patients' willingness to answer study questions and participate in the psychosocial supportive intervention with the mental health professional will indicate their consent.

Patients will be asked to complete the following 9 validated questions:

1. Please rate your pain by choosing the number that tells how much pain you have right now? (from the Brief Pain Inventory; Cleeland, 1994)
2. How unpleasant is your pain right now? (Garland et al., 2017)
3. How much do you want to take pain medicine right now? (Garland et al., 2014)
4. How anxious are you right now? (Lang et al., 2006)
5. In the past 15 minutes, I experienced all things seeming to unify into a single whole. (Hanley, Nakamura & Garland, 2018)
6. In the past 15 minutes, I experienced all sense of self and identity dissolve away. (Hanley, Nakamura & Garland, 2018)
7. In the past 15 minutes, I felt surrounded and filled with a blissful warmth or energy. (Hanley, Nakamura & Garland, 2018)
8. In the past 15 minutes, I had moments when I felt alert and aware. (Tanay & Bernstein, 2013)
9. In the past 15 minutes, I watched my thoughts, feelings, and sensations without getting lost in them. (Baer et al., 2006)

Once these questions are answered, the mental health professional will provide one of three study interventions: A) 15 minute mindfulness session, B) a 15 minute therapeutic suggestion session, or C) a 15 minute CBT psychoeducation session.

Following the 15 minute psychosocial supportive intervention, participants will be asked the same 9 questions listed above.

Once per month, the UU Hospital data warehouse will provide the PI with the following pre-, peri-, and postoperative data for each Joint Academy attendee: patient age, gender, admitting diagnosis, CAPA scores, PROMIS scores, dosages of pain medicine received during hospital stay (Tramadol, Oxycodone, Hydrocodone, Morphine, Fentanyl, Hydromorphone, Acetaminophen, Ketorolac, Ibuprofen, Naproxen, Celecoxib), heart rate, blood pressure, post-acute care, and hospital readmission

Provide a summary of the statistical methods, data analysis, or data interpretation planned for this study. Factors for determining the proposed sample size (e.g., power) should be stated.

Effects of treatment on outcomes (change in pain severity, pain unpleasantness, anxiety, pain medication desire, and physical functioning) will be evaluated using linear mixed models where outcome variables are regressed on intervention group (mindfulness vs. hypnotic suggestion vs. cognitive-behavioral psychoeducation) after covarying baseline values. Models will also be adjusted for age, sex, proximity of outcome measurement to surgery, and admitting diagnosis. All tests and CIs will be 2-sided and statistical significance will be defined as a *P* value less than .05. All linear models will be conducted using SPSS version 25.

Little's MCAR test will be used to determine if data are Missing Completely at Random (an ideal that is rarely met with longitudinal data). There is no definitive test for Missing at Random (MAR), which describes data that are random conditional on observed data. We will use maximum likelihood estimation procedures to deal with missing data according to an intent-to-treat philosophy that is robust against the most common patterns of missing longitudinal data. Maximum likelihood estimation is based on all data observations; no values will be deleted or imputed.

A priori power analysis was conducted using Optimal Design. An estimated total sample size of 250 participants in 47 cohorts will be necessary to detect an overall between-group effect on baseline-adjusted outcomes ($f=0.25$, or of small size) with 80% power, two-sided $p < 0.05$.

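### The assignment is disclosed to the mental health professional before patients are approached and consented, and no concealment is described, so enrolment can depend on the arm

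*Combined protocol and SAP*

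**What the plan says.** All references are to the combined protocol and SAP.

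- **Randomization (procedures section).** Joint Academy patients are allocated 1:1:1, with the mechanism given as "using a pre-generated random number table, determining the type of psychosocial supportive intervention introduced during the" (the text goes on to name the session). The next sentence reads: "The visiting mental health professional will be notified of the random assignment prior to Joint Academy".
- **Contact (procedures section).** Once patients attend, the plan is that "the mental health professional makes will make contact with the potential participant, the patient will be presented with a fact sheet about the study", and the mental health professional discusses it with the patient.
- **Consent (recruitment section; the procedures section says the same).** "Their willingness to answer study questions and participate in the psychosocial supportive intervention with the mental health professional will indicate their consent".
- **Baseline, then session (procedures section).** The patient answers 9 questions. "Once these questions are answered, the mental health professional will provide one of three study interventions".
- **Exclusion (Participants section).** The only listed criterion is "Altered mental status due to delirium, psychosis, or pharmacological sedation as determined by clinical assessment conducted by a mental health professional". When this is assessed, and whether the assessor knows the arm, is not stated.
- **Staff (purposes section).** The trial sits in an existing programme "which currently employs mental health professionals to teach patients preparing for surgery pain management strategies".
- **Analysis (statistical methods section).** Outcomes are adjusted for their baseline value, and "Models will also be adjusted for age, sex, proximity of outcome measurement to surgery, and admitting diagnosis". Missing data are handled by maximum likelihood.

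The document mentions no envelopes, central allocation, recruiter unaware of the arm, or log of patients approached and declining.

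**The concern.** Randomization makes the arms comparable only if entry to the analysed group does not depend on the arm. Here the arm is known to at least one member of the study staff before anyone is invited, and that person's role is the one that presents the study. Consent is informal and follows a conversation. The stated hypothesis is directional: mindfulness and suggestion are expected to do better than CBT psychoeducation. Without any intent to do so, someone who knows the arm can present the study more or less warmly, or judge a borderline mental state differently.

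The outcomes most exposed are the immediate ratings of pain, unpleasantness, anxiety and desire for medication. They are self-rated, and they exist only for patients who agree to answer. If the patients who agree differ between arms in expectancy or attitude to the technique, part of any difference between arms reflects who enrolled. Without counts of patients approached and declining by arm, the trial could not later show that this effect was small.

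**Working it through.** **1. Order of steps.** The procedures section answers a prompt asking for a chronological account, so its order can be taken as intended:

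| Step | Who | Arm already disclosed? |
|---|---|---|
| Assignment drawn from table | not stated | - |
| Notification | visiting mental health professional | yes, from here on |
| Contact, fact sheet, consent | the mental health professional | yes |
| 9 baseline questions | patient | yes |
| 15-minute session | the mental health professional | yes |

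The exclusion assessment has no stated place in this order.

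**2. What can go wrong under each reading of the randomized unit.** The 47 cohorts in the power statement suggest allocation by session (250/47 = 5.3 patients each); the wording that patients are randomized suggests allocation by patient.

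- By patient: exclusion, invitation and encouragement can each vary with the arm.
- By session: everyone present shares an arm, so there can be no selective invitation by arm within a session. Encouragement and uptake can still differ between sessions.

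**3. Whether the analysis removes it.** The covariates do not include expectancy or attitude to the technique. Maximum likelihood deals with missing values among enrolled patients. It does nothing for patients who never enrolled.

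**4. Illustration of size.** The documents give no approach, refusal or enrolment rates, so every input on selection below is assumed.

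- *Effective N.* The overall F test of 3 groups (2 and N-3 df, f = 0.25, alpha 0.05) has power 0.7995 at N = 157 and 0.8022 at N = 158, so 158 is used. The plan's 250 would have 95% power without clustering. No intraclass correlation is given, so 250 can be neither confirmed nor called wrong, and nothing here rests on it.
- *Selection.* A fraction x = 0.10 or 0.20 of an arm is lost strictly from one end of the expectancy distribution. Mean expectancy of those remaining moves by k = phi(z_x)/(1 - x): 0.195 SD at 0.10 and 0.350 SD at 0.20.
- *Outcome shift.* s = r x k, where r is the correlation of expectancy with the outcome after all covariates, assumed 0.2 or 0.4.
- *One arm shifted by s.* f = s x sqrt(2)/3, so the noncentrality is 158 x 2s^2/9.
- *Two arms shifted in opposite directions by s.* The noncentrality is 158 x (2/3) x s^2.

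| r | x | s (SD) | Type I error, one arm loses lowest | Type I error, another arm also loses highest |
|---|---|---|---|---|
| 0.2 | 0.10 | 0.039 | 5.4% | 6.2% |
| 0.2 | 0.20 | 0.070 | 6.3% | 9.0% |
| 0.4 | 0.10 | 0.078 | 6.6% | 10.0% |
| 0.4 | 0.20 | 0.140 | 10.4% | 22.8% |

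Check of the last row: 158 x 2 x 0.140^2/9 = 0.688 gives 10.4%; 158 x (2/3) x 0.140^2 = 2.064 gives 22.8%.

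*Milder versions, over r = 0.2 to 0.4.* If refusal correlates only 0.5 with expectancy, s is halved and the one-arm figures are 5.1-6.3%. If every arm loses 10% and one loses 20%, s = r x (0.350 - 0.195) = 0.031 to 0.062 and the figures are 5.2-6.0%.

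The calculation treats the arms as equal in size and uses the patient-level test. With 44 denominator df, to reflect 47 cohorts, the 10.4% becomes 10.2%.

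**The case against.** **The recruiter may be someone else.** The text never says that the visiting professional who is notified is the person who approaches patients, and the programme employs several professionals. A reader might infer that the plan expressly has one informed person recruit. It does not; that is only the natural reading, since one role is described for approach and delivery and no separate recruiter appears. This part of the objection stands, but it leaves the absence of concealment untouched.

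**Discretion is limited.** The exclusion criterion is a specified clinical state, not a general judgement of suitability, and no step lets the professional choose whom to invite. If allocation is by session, selective invitation within a session cannot occur. This stands and narrows the route under cohort allocation to encouragement and uptake between sessions.

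**The effect may be small.** In the milder cases type I error stays near 5-6%. This also stands. The figures cannot serve as a case that the bias is large. Equally, a reader might take 10.4% as a ceiling; it is not, because opposite selection in two arms gives up to 22.8% from the same inputs.

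**Some outcomes may be protected.** The warehouse extract is planned for every Joint Academy attendee, so postoperative function may be comparable as assigned whether or not patients consented, subject to completeness, which is not stated. A reader might infer that all outcomes are equally exposed; the documents do not support that.

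**Advance notice may be needed for preparation.** This is possible, and the documents do not say whether each professional can deliver all three sessions. It bears on the cost of the fix, not on whether the gap exists.

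**Conclusion.** The concern holds as a gap in allocation concealment. It is more than missing detail: the plan states a sequence which, if followed, makes the arm known to study staff before enrolment. The bias is possible, not demonstrated, and its size and direction are unknown. It bears mainly on the immediate self-rated outcomes. The range of 5.4-22.8% across the two selection patterns rests wholly on assumed loss rates, assumed correlations and strict ordering of losses, and bounds nothing. The case for change is procedural: the sequence permits arm-dependent enrolment, the planned analysis cannot undo it, and the order of steps makes it simple to close. It should be fixed; confidence is medium, because the identity of the recruiter and the unit of randomization are not express.

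**What to change.** 1. In the procedures section, replace advance notification with this rule: the assignment is withheld until eligibility, consent and the 9 baseline questions are complete for the randomized unit (everyone present if by session, the individual if by patient). It is then revealed just before the 15-minute session, for example by sealed, sequentially numbered opaque envelope.
2. Record the numbers attending, excluded, approached and declining, and report them by arm.
3. Consent is defined as willingness both to answer and to take part. State how a patient who answers the baseline questions and then declines the revealed session is counted.

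**Cost.** Consent and baseline already come before the session, so no visit or measurement is added. The change needs protocol wording, a log, and one envelope per randomized unit: 47 if by cohort, about 250 if by patient.

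**Downside.** The professional must be prepared to deliver any of the three sessions. If that is not possible, an existing team member unaware of the assignment would have to handle eligibility, consent and baseline, at some cost in staff time at each Joint Academy.

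### Five unranked outcomes are each tested at .05 with no primary outcome, testing order, adjustment or success rule, so the stated 5% and 80% describe one overall test on one unnamed outcome

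*Combined protocol and SAP*

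**What the plan says.** The statistical methods summary names five outcomes side by side: "change in pain severity, pain unpleasantness, anxiety, pain medication desire, and physical functioning". Each is "regressed on intervention group (mindfulness vs. hypnotic suggestion vs. cognitive-behavioral psychoeducation"), that is, on a three-level factor with 2 degrees of freedom. One threshold covers everything: "All tests and CIs will be 2-sided and statistical significance will be defined as a" P value below .05. The power statement in the same section is for 250 participants in 47 cohorts to "detect an overall between-group effect on baseline-adjusted outcomes", with a single effect size (f = 0.25), a single alpha and a single power of 80%. It does not say which outcome.

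The hypothesis under Study Purposes and Objective is more specific: "Mindfulness training and therapeutic suggestion will decrease pain, anxiety, and pain medicine desire as well as increase postoperative physical function" by significantly more than CBT psychoeducation does. Aim 1 is broader and concerns the "differential effects of a brief mindfulness training session versus therapeutic suggestion session or a CBT psychoeducational session". In the procedures, four of the five outcomes are single-item ratings taken at one sitting, since after the session "participants will be asked the same 9 questions listed above".

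No section ranks the outcomes, orders or adjusts the tests, specifies a pairwise contrast, or says what result would count as success.

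**The concern.** There are two gaps between what is powered and what is claimed.

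The first is across outcomes. Five tests at .05 do not carry a 5% error rate as a set, and nothing says which of them decides the trial.

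The second is within an outcome. The overall 2-df test has no direction. It can be significant when only one arm differs from CBT, when an arm is worse than CBT, or when CBT lies between the other two. It therefore cannot by itself show that both arms beat CBT. That needs two contrasts, and Aim 1 can be read as adding a third (mindfulness vs suggestion).

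The success rule is thus open in both directions. A lenient reading (any significant result) usually inflates error. A literal reading of the hypothesis (both arms, every outcome) protects error but leaves power well below 80%. Since the plan commits to neither, the rule could be settled after results are seen.

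**Working it through.** **The plan's own figure.** Power of the three-group test is P(F′ > F₀.₉₅), where F′ is noncentral F with 2 and N−3 df and noncentrality N·f². With f = 0.25 and alpha .05, 80% power needs N = 158 without clustering, and 250 would give 95%. With 250/47 = 5.3 people per cohort and design effect 1 + (5.3−1)·ICC, 250 gives 80% at an ICC of about 0.12 (44 denominator df) to 0.14 (247 df). The document prints no ICC, so 250 cannot be reproduced from its inputs alone. That does not affect this point: 80% for one overall test is taken as given below, which corresponds to noncentrality 9.63 in the large-sample (chi-square, 2 df) form.

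**Assumptions.** Equal arms (allocation is 1:1:1), normal approximation, valid standard errors, five outcomes with a common correlation. The correlation is not in the document. The range 0 to 0.7 is used, with 0.9 as a further case; 0 is a bound, because four outcomes are ratings from one sitting. Results are from simulation with 500,000 replicates and arms shared across contrasts.

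**Chance of at least one false positive when no arm differs on any outcome.** At correlation 0 the overall tests give 1 − 0.95⁵ = 22.6%.

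| What counts as a finding | 0 | 0.5 | 0.7 | 0.9 |
|---|---|---|---|---|
| Any of 5 overall tests | 22.6% | 18.7% | 15.2% | 10.5% |
| Any of 10 two-sided contrasts with CBT | 37.8% | 31.2% | 25.5% | 17.9% |
| Any of 15 pairwise contrasts | 47.9% | 39.5% | 32.5% | 23.2% |
| Contrasts with CBT only after a significant overall test, favourable only | 10.0% | 8.1% | 6.5% | 4.5% |

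With the four same-sitting ratings correlated 0.7 and functioning correlated 0.2 with each, the four rows are 17.5%, 29.4%, 37.4% and 7.6%.

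**Power for the hypothesis on one outcome, overall test at 80%.** Scale each arm mean to unit variance. If both arms are equally better than CBT, the centred means are (a, a, −2a) with 6a² = 9.63, so a = 1.267. Each contrast with CBT has standardized effect 3a/√2 = 2.69 and power Φ(2.69 − 1.96) = 77%, or 72% if it also requires the overall test. The two contrasts correlate 0.5, and both are significant 64% of the time.

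Other patterns with the same overall power of 80%:
- One arm has half the other's effect: standardized effects 3.10 and 1.55, both significant 33% of the time.
- Only one arm works: 2.69 and 0, both significant 2.5%.
- CBT midway between the other two: 1.55 and −1.55, both significant 0.02%.

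In the last two patterns the hypothesis is false. The overall test is still significant 80% of the time, so it does not stand in for the hypothesis.

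**Power if both arms must beat CBT on all five outcomes**, both arms equally better on every one: 11.0%, 28.4%, 37.2% and 49.0% at correlation 0, 0.5, 0.7 and 0.9.

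**The case against.** The strongest reply is that the hypothesis is directional, so wins for CBT should not be counted as false positives. Counting only favourable contrasts, without a gate, the 38% to 26% becomes 21% to 13% (9% at 0.9). That is fair as arithmetic, and 38% should be read as the two-sided figure. But the plan declares its tests two-sided, and the favourable-only figure still exceeds 5%.

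A second reply is that success could be judged outcome by outcome, with both arms required. Under no effect anywhere, that happens on at least one outcome in only 2.3% to 1.7% (1.1% at 0.9). But if one arm works strongly on every outcome and the other does nothing, the same rule wrongly credits both arms on at least one outcome in 12% to 7% (about 5% at 0.9).

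Two further points stand in part. The count of 15 contrasts is an outer bound, because mindfulness vs suggestion appears in Aim 1 but carries no hypothesis. And the plan does narrow the field: of all the data collected, only five outcomes enter the treatment-effect analysis, with one model form and one covariate set. The open choice is therefore about success rules within that list, not about the whole dataset.

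Finally, requiring both contrasts lowers power to 64%. That is true and is stated as a cost below. It is a property of the hypothesis as written, which the 80% never described.

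**Conclusion.** The point holds. For a single overall test on a single outcome, 5% and 80% are coherent targets; the plan does not say which test or outcome that is, and the hypothesis needs something else. If any significant overall test counts, the false-positive chance is 23% to 15% for correlation 0 to 0.7, and still about 10% at 0.9. Counting contrasts raises it on most readings. The lenient reading that stays near 5% is favourable contrasts gated on the overall test, with correlation near 0.9. If both arms must win everywhere, power is 11% to 37% (49% at 0.9) rather than 80%. These sizes rest on the assumed correlations, equal arms, valid standard errors and, for power, overall power of 80% on every outcome. The absence of a success rule rests on none of them. It should be corrected before analysis.

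**What to change.** Add the following to the statistical section before analysis.

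1. Name one primary outcome; which one is the sponsor's choice.
2. Test its 2-df group effect at .05. Only if that is significant, test mindfulness vs CBT, suggestion vs CBT and mindfulness vs suggestion on it, each at .05. With exactly three arms this holds 5% within that outcome.
3. State that the hypothesis is supported only if both contrasts with CBT are significant in the predicted direction.
4. Label the other four outcomes secondary and choose one option:
   - **A.** Report them as supportive, with estimates and confidence intervals and no confirmatory claim.
   - **B.** Test them only after both primary contrasts with CBT succeed, using Holm at .05 over the 4 × 2 = 8 secondary contrasts with CBT. In simulation (300,000 replicates) total error for contrasts with CBT was at most 5.0% in every scenario tried.
5. Under B, if mindfulness vs suggestion on the primary outcome is also to be confirmatory, move it into the Holm family (nine contrasts). Testing it separately at .05 takes total error to about 10% at most (9.5% at correlation 0, 7.0% at 0.9, when both arms strongly and equally beat CBT on the primary and no secondary effect exists).
6. Under either option, state that mindfulness vs suggestion on secondary outcomes is descriptive.

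The change is wording. The primary overall test keeps .05, so 250 need not change for this reason. The plan should state the price: with overall power of 80% and equally effective arms, one gated primary contrast has about 72% and both have about 64%, or about 33% if one arm has half the other's effect. Under B, the gate to secondary tests opens only that often, and secondary thresholds are stricter.

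If the sponsor wanted 80% for both primary contrasts, the sample would have to grow by a factor of about 1.35 (1.354 × 250 ≈ 339) with equal arms, and about 3.3 with a half-size arm, at the same cohort size. That is a separate decision. The simpler alternative of Bonferroni over the five overall tests (.05/5 = .01 each) would cut power per outcome to about 57% to 59% at 250 and still leave the contrasts unspecified.

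### The power statement calls f=0.25 a small effect, but with three equal arms it is a difference of at least 0.53 adjusted SD; the label, more likely than the number, needs correcting

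*Combined protocol and SAP*

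**What the plan says.** The final paragraph of the statistical methods section contains the plan's only sample-size justification: "An estimated total sample size of 250 participants in 47 cohorts will be necessary to detect an overall between-group effect on baseline-adjusted outcomes". It gives the effect as f=0.25 and adds "or of small size) with 80% power", at a two-sided 5% level. It does not define a small effect, does not express the effect in SD units or scale points, and reports neither an intracluster correlation (ICC) nor a covariate R².

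Three other statements fix the setting. The procedures describe three arms with "allocation ratio 1:1:1) using a pre-generated random number table". The analysis model compares groups "after covarying baseline values", which is why the effect is on an adjusted scale. The Aim 1 hypotheses expect both active arms to improve outcomes "to a significantly greater extent than CBT psychoeducation", so the pattern of means closest to the hypothesis has both active arms equally far from CBT.

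**The concern.** One effect is described by a number and by a word, and the two point to different sizes. By the usual convention f=0.10 is small and f=0.25 is medium. The documents quote no convention, so the check should not rest on that benchmark alone. The more basic difficulty is that a gap of more than half an adjusted SD between the most different arms is not naturally called small.

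At stake is how the trial's sensitivity is understood. All three arms receive an intervention, so differences between them may be modest and a non-significant result is a realistic possibility. A reader who relies on the label could take such a result as evidence against small differences, which 250 participants cannot supply on the scale the sentence names.

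**Working it through.** **Inputs from the documents.** N=250; 47 cohorts (mean size m = 250/47 = 5.32); three arms, 1:1:1; alpha 0.05; f=0.25; power 80%; omnibus test after baseline adjustment. **Not given, so assumed where used:** ICC, covariate R², and whether whole sessions are the unit of assignment.

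**Method.** Noncentral F test with 2 numerator df and noncentrality N·f²/DE, where DE = 1 + (m − 1)·ICC = 1 + 4.32·ICC. Denominator df are taken at two extremes: 44 (47 − 3) and 247 (250 − 3). Paired results below are in that order.

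**1. The plan's own figure.** With no clustering, f=0.25 needs 158 participants (159 for equal arms). At N=250 the noncentrality is 250 × 0.0625 = 15.625 and power is 93.8% / 95.0%, so 250 includes a margin. Power falls to 80% at an ICC of 0.119 / 0.139 with equal cohort sizes:
- ICC 0.119: DE = 1.51, noncentrality 15.625/1.51 = 10.3
- ICC 0.139: DE = 1.60, noncentrality 15.625/1.60 = 9.8

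The stated 250, 47, f=0.25 and 80% can therefore fit together, but this cannot be verified without the ICC.

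**2. What f=0.25 means with three equal arms.** For a largest pairwise difference d in adjusted SD:
- both active arms equally far from CBT: f = d·√2/3, so d = 0.25 × 3/√2 = 0.530
- means evenly spaced: f = d/√6, so d = 0.25 × √6 = 0.612

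The first is the minimum over all positions of the middle mean.

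**3. Power at N=250 for smaller effects, no clustering.**

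| f | Noncentrality | Power, df 44 | Power, df 247 |
|---|---|---|---|
| 0.10 | 2.5 | 25.8% | 27.1% |
| 0.15 | 5.625 | 52.5% | 55.0% |
| 0.20 | 10.0 | 78.7% | 81.0% |
| 0.25 | 15.625 | 93.8% | 95.0% |

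The smallest f with 80% power is 0.203 / 0.198. A positive ICC under session-level assignment would raise it. For f=0.10, 80% power would need about 967 participants before any clustering.

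**4. If the number were the slip.** Suppose a standardized difference of 0.25 was written as f:
- equal difference from CBT: f = 0.25 × √2/3 = 0.118, power 34.5% / 36.2%
- evenly spaced: f = 0.25/√6 = 0.102, power 26.7% / 28.1%

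On the adjusted scale with no clustering that is 27-36%, not 80%.

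**The case against.** The strongest reply is that no stated number is shown to be wrong. The documents never define a small effect, f=0.10 appears nowhere in them, and a reader who knows f sees 0.25 printed beside the adjective. This stands in part: the 26-27% is power for an effect the plan does not name as its target, and it depends on an outside benchmark. But the conflict does not need that benchmark. For any definition of small below f of about 0.20, the sentence fails on its own scale even without clustering.

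A second reply is that the label may refer to the raw scale. After the session "participants will be asked the same 9 questions listed above", so the before-after correlation may be high for those items. At an assumed R² of 0.7 or 0.8, 0.53 adjusted SD is 0.53 × √0.3 = 0.29 or 0.53 × √0.2 = 0.24 raw SD, which could loosely be called small. However, the sentence names baseline-adjusted outcomes and reports no R². If a raw f=0.10 was intended, 80% power needs an R² of 0.74-0.76 with no clustering.

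Two stronger readings are tempting and are not supported. A reader might infer that the trial is too small. The documents do not show this: step 1 finds 250 sufficient for f=0.25 up to an ICC of about 0.12-0.14. A reader might also infer that 0.25 was a standardized difference and that true power is about 30%. Nothing in the documents says so, and that reading fits the stated 80% worse than f=0.25 does.

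It is also fair to say that the plan promises two-sided confidence intervals, which would show what a null result excludes. That lessens the risk of misreading but does not correct the sentence.

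**Conclusion.** The point holds as a mismatch between value and label in the plan's only sample-size justification. On the baseline-adjusted scale that the sentence names, f=0.25 is at least 0.53 adjusted SD. The design reaches 80% power only from f of about 0.20, and power at f=0.10 is 26-27%. The label is the likelier error, because the number can be reconciled with N, cohorts and power at a plausible ICC; the documents do not prove it.

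These figures rest on equal arms and, except where an ICC is given, no clustering. The ICC range is conditional. The study purposes section describes a comparison made "by randomly assigning patients to one of the three approaches", while the procedures state "The visiting mental health professional will be notified of the random assignment prior to Joint Academy", which suggests assignment by session without saying so. The range also assumes equal cohort sizes. Confidence is high that the value and the label conflict, and lower on which of them is wrong. The statement should be corrected; the design is not invalidated.

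**What to change.** Keep N=250. Confirm from the Optimal Design record which effect-size metric was entered.

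- **If f=0.25 was entered:** delete the reference to small size and state the effect as *f=0.25 on the baseline-adjusted scale, about 0.53 adjusted SD if both active arms differ equally from CBT*.
- **If another metric was entered,** for example a standardized difference of 0.25: correct the value and restate the power it gives for the three-arm design (27-36% on the adjusted scale with no clustering, in that example).

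Reporting the ICC and R² used, and adding a note that a non-significant result does not exclude effects near f=0.10, would be useful but are optional; the label conflict can be corrected without them.

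The cost is one look-up and one or two rewritten sentences. Randomization, outcomes and analysis do not change. The stated sensitivity becomes less favourable.
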